- 4.6 **Scoring of screening instrument:** We have incorporated a validated KPSC scoring algorithm for the PHQ screening, based on the PHQ scoring instructions, to ensure correct scoring and appropriate referral. Results will group a patient into one of 3 categories: 1) Low score: referral to Health Education (e.g., stress reduction classes, mind/body classes and sleep improvement classes, etc.); 2) Moderate score: referral to Depression Care Management (a program of KPSC Complete Care, see 4.6.1) or local oncology social worker to discuss referrals and individual options; 3) High score: immediate referral to Behavioral Health/psychiatry. In the event of endorsement of suicidal ideation (regardless of overall score), an in-person or telephone consultation with a behavioral health provider will be initiated; escort to behavioral health and/or the emergency department will be decided by the behavioral health provider and medical oncologist. A detailed protocol and training will be provided to all intervention sites.
- 4.6.1 **Complete Care Depression Program.** The Depression program is an integrated, regionally supported program based in primary care and using a population based approach to: 1) identify and treat depression based on evidence and best practices; 2) offer screening and assessment models (i.e. integrated into current care processes); and 3) advance treatment care models (both core and customizable components). The goal of the program is to improve the care of adult patients with co-morbid conditions by the appropriate screening, assessment, and treatment of depression as an extension of Primary Care/Care Management in conjunction with Behavioral Health. Depression Care Specialists provide treatment, including medication initiation and management, education, problem solving treatment and behavioral activation. Under a program redesign, new workflows were developed, which typically begin with the administration of the PHQ.
- 4.7 **Referral pathways:** Per guideline recommendations, we will leverage referral pathways to behavioral health services which may include the oncology social worker (if such a resource is available at the site), depression care managers, and psychiatry/behavioral health. This approach leverages existing resources from the KPSC Complete Care Depression Program.

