## **5.0 DATA SOURCES**

We will obtain and compare data from the sources described below for patients from both the intervention and the control condition.

- 5.1 Distress screening: We will use a recommended distress screening instrument (PHQ), which is part of the electronic health record.
- 5.2 Referral: We will access referral data using Tapestry, a database linked to the KPSC electronic medical record that records all referral activities, including those to behavioral health services. We will collect referral data retrospectively at completion of the 12 month screening intervention. We will collect and compare the number of referrals to relevant behavioral health services, including: depression care management, psychiatry, psychology, social work, and health education. We will also obtain information on referral initiation and completion (e.g., patient visit with referred provider).
- 5.3 Utilization of health care services: To compare patient utilization of health services between intervention and control sites, we will capture utilization of health services from our electronic medical record using Current Procedural Terminology (CPT) and International Classification of Disease (ICD) codes as appropriate. We will collect utilization data retrospectively at 18 months after the initiation of the distress screening program in the intervention centers. This will provide utilization data for a maximum of 18 months. We will capture number of emergency department visits, hospitalizations, urgent care visits, primary care and oncology visits, and behavioral health visits, including interactions with psychology, psychiatry, and social workers (in-person, email, and telephone contact).
- 5.4 Covariates and breast cancer treatment data: We will collect covariate information from the electronic health record and data from the KPSC tumor registry. Covariates from the registry will include date of diagnosis, age at diagnosis, stage of disease, estrogen receptor/progesterone receptor/human epidermal growth factor receptor 2 status, treatment types and dates including use of Herceptin and aromatase inhibitors, laterality, tumor size and histology, sequence number, and treating medical center. Covariates from the electronic record will include age, date of birth, gender, race/ethnicity, and geocoded census tract education and income.

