## **7.0 SELECTION AND WITHDRAWAL OF SUBJECTS**

- 7.1 Inclusion Criteria: All patients with a visit to medical oncology for a new diagnosis of breast cancer at a study site are eligible for inclusion, with no exclusions due to gender, age, stage of disease, sequence of disease, comorbidity, spoken or written language, or other demographic or cancer characteristic.
- 7.2 Exclusion Criteria: Non-breast cancer patients.

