and large ICC (0.2 and 0.01, respectively). Given that we can expect 50 to 300 newly diagnosed breast cancer patients per center, we should be adequately powered to detect effect sizes as small as 0.2, given ICCs no greater than 0.007. This is a lower bound on our power, since we expect to have as many as 200 more patients at some medical centers, and so our power is most likely greater than reported here.

- 14.2 Statistical analysis plan: All variables will be described with summary statistics appropriate for measurement type, such as frequency and percent, mean, median, standard deviation, minimum, and maximum. Patterns of missing values will be examined and evaluated for randomness using the method described by Enders. Diagnostic plots and inferential tests for tenability of assumptions will be evaluated for our primary and secondary outcomes, and appropriate remedial methods (e.g., Box-Cox transformations) applied where required. We will analyze referral and utilization outcomes as the total amount of services used during the study period, and use said diagnostic tests to determine the best modeling strategy for examining relationships with relevant demographic and clinical characteristics, exploring potential disparities by race/ethnicity and socioeconomic status. If necessary, we will analyze relationships with referral and utilization outcomes using Poisson or Negative Binomial regression models. We will use an intent-to-treat analysis, including data on all newly diagnosed patients in the intervention and control groups without regard to their screening status, appropriate for a cluster RCT.

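### No pre-diagnosis behavioral health or utilization measure is planned, which costs precision and leaves the referral and utilization comparisons open to chance imbalance with 3 centers per arm

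*Combined protocol and SAP*

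**What the plan says.** Section 7.1 admits every patient seen in medical oncology for a new breast cancer diagnosis, "with no exclusions due to gender, age, stage of disease, sequence of disease, comorbidity". Patients already receiving mental health care are therefore in the cohort. Section 4.6.1 describes an existing regional depression program run from primary care, which is also one of the trial's referral destinations.

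Section 5.4 lists the covariates in two groups. From the registry: "Covariates from the registry will include date of diagnosis, age at diagnosis, stage of disease", followed by receptor status, treatment and tumor items. From the health record: "Covariates from the electronic record will include age, date of birth, gender, race/ethnicity, and geocoded census tract education and income". Neither group contains anything on mental health or service use before diagnosis, and no other section adds it.

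On outcomes, section 5.2 states: "We will collect and compare the number of referrals to relevant behavioral health services". It illustrates completion of a referral as a visit to the provider concerned. Section 5.3 states: "We will collect utilization data retrospectively at 18 months after the initiation of the distress screening program in the intervention centers", and then: "This will provide utilization data for a maximum of 18 months". Section 14.2 states: "We will analyze referral and utilization outcomes as the total amount of services used during the study period". It names no baseline term for these models. To study identification, section 14.2 sets patients with high distress on the FACT-B against patients referred to psychiatry or psychology. The surveys start at 3 months, so there is no patient-reported baseline either.

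**The concern.** A patient already under psychiatry, psychology or depression care at diagnosis will usually go on generating visits, and perhaps referrals, in either arm. Study-period totals mix this activity with whatever the program adds. Three consequences follow:

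- **Variance.** Past use of a service usually predicts later use. Leaving it out of the model puts explainable variation into the error term.
- **Chance imbalance.** Randomizing six centers balances prior care only on average. With three per arm, one center with many patients already in care can move an arm total, and without a baseline measure nobody can see that it did.
- **Interpretation.** In the FACT-B comparison, a distressed patient who is already in care and has no new referral looks missed. A routine follow-up visit could also be read as completing a referral.

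**Working it through.** The documents give no prevalence of prior care and no figure on this point, so there is nothing of the plan's own to reproduce. What follows sizes the exposure.

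**Inputs from the documents.** 3 centers per arm and 600 patients per arm (section 3.0). This gives 1,200 / 6 = 200 per center on average; equal sizes are a simplification, since section 14.1 expects 50 to 300. The ICC of 0.007 is the limit that section 14.1 attaches to its power claim.

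**Assumptions.** 10% to 30% already in care; ICC for prior care of 0.007 to 0.05; 4 to 8 continuing visits per patient; a program that newly links 5% to 10% of patients at 3 visits each; correlation of 0.3 to 0.7 between prior and later use.

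**Step 1: chance difference in prior care between arms.** Design effect DE = 1 + (200 − 1) × ICC, which is 2.393 at 0.007 and 10.95 at 0.05. SE = √(2p(1 − p) × DE / 600). For p = 0.10 and ICC 0.007: √(2 × 0.09 × 2.393 / 600) = 0.0268, and 1.96 × 0.0268 = 0.053.

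| Prior care (assumed) | 95% range, ICC 0.007 | 95% range, ICC 0.05 |
|---|---|---|
| 10% | ±5.3 points | ±11.2 points |
| 20% | ±7.0 points | ±15.0 points |
| 30% | ±8.0 points | ±17.2 points |

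**Step 2: the same difference in visits (10%, ICC 0.007).** One standard error is 600 × 0.0268 ≈ 16 patients, or 64 to 129 visits at 4 to 8 each. The edge of the 95% range is 600 × 0.053 ≈ 32 patients, or 127 to 254 visits. The assumed program effect is 600 × 0.05 × 3 = 90 to 600 × 0.10 × 3 = 180 visits. An ordinary chance imbalance is thus of the same order as a plausible effect, under these assumptions.

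**Step 3: precision from adjustment.** In a linear model, a baseline with correlation r multiplies individual-level residual variance by 1 − r²: 0.91, 0.75 and 0.51 for r = 0.3, 0.5 and 0.7. Not all of the variance of an arm mean is individual-level. At ICC 0.007 the within-center share is 0.993 / 2.393 = 0.415. If adjustment reduces that share only, the factor is 1 − 0.415r²: 0.96, 0.90 and 0.80. If it reduces the between-center share equally, the full 0.91, 0.75 and 0.51 apply. The gain lies somewhere between and depends on how far centers differ because of prior care.

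**Step 4: the identification comparison.** Two patients with the same high FACT-B distress and no referral to psychiatry or psychology fall in the same cell, whether one is already under psychiatry or neither is. None of the variables in section 5.4 separates them.

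**The case against.** The strongest reply is that the randomized comparison is intact, and most of that reply stands. Continuing care occurs in both arms, the data sources are the same, centers are randomized, and the analysis is intent-to-treat. The absolute difference in totals is unbiased in expectation. Chance imbalance is sampling error, which an analysis that accounts for center carries in its standard error. Section 5.4 says what the covariates will include, section 14.2 leaves room for relevant clinical characteristics, and the record could still supply the history. The accurate statement is therefore that it is not pre-specified, rather than that it cannot be had.

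A reader might infer more than the documents support:

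- **That the objectives concern newly identified distress and so cannot be answered.** The aims speak of identifying distressed patients, without limiting this to new cases. Total differences remain estimable.
- **That continuing care contaminates the primary outcome.** Section 4.10 requires screening and referral on the PHQ score, and section 12.0 ties the PHQ to an oncology visit. Continuing visits alone cannot satisfy that.
- **That known patients will be miscounted because they are not referred again.** In section 4.6, "Results will group a patient into one of 3 categories" on score alone, with no stated exception for patients already in care. Whether they should be re-referred is a clinical matter on which this review takes no position.
- **That continuing care swamps the signal.** Assuming 5% to 20% in care at 4 to 8 visits gives 120 to 960 continuing visits per arm. Against 180 or 90 new ones, that is 120 / 300 = 40% to 960 / 1,050 = 91% of the sum. This is a proportion within one arm and says nothing about the difference between arms.

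The reply does not remove the lost precision, the undetectable imbalance with 3 against 3 centers, or the ambiguity in the FACT-B comparison.

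**Conclusion.** The point holds as an inexpensive improvement to a comparison that is valid in expectation. The plan names no pre-diagnosis measure for outcomes that past use is likely to predict, in a cohort that includes patients already in care. At the plan's own ICC limit and an assumed 10% prevalence, prior care could differ by about ±5.3 points between arms by chance. Over the assumed grid the range runs from ±5.3 to ±17.2. Adjustment with an assumed correlation of 0.5 would reduce the variance of the comparison by about 10% to 25%. Prevalence, visits, correlations and the higher ICC are all assumptions. The visit counts are illustrations only. That the measure is absent from the plan rests on the text alone.

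**What to change.** - **Section 5.4:** add from the same electronic record, for the 12 months before diagnosis, any depression or anxiety diagnosis, any behavioral health contact, and counts of each utilization type in section 5.3. The registry's diagnosis date can anchor the look-back. Section 5.3 measures its window from program start, so also state when each patient's outcome count begins, so that the look-back and the outcome do not overlap.
- **Section 14.2, models:** include the prior-year count of the same service as a covariate in each utilization model.
- **Section 14.2, reporting:** as a supplementary analysis, show identification, referral, completion and behavioral health visits by prior-care status.
- **Section 4.10:** leave the intent-to-treat primary outcome unchanged, and build no rule into it about patients already in care.

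The cost is one more retrospective extract, a check that the consent waiver covers the look-back, and a category for unknown history for patients with under 12 months of prior membership. The definitions should be fixed before any comparison by arm is seen.

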## **6.0 DRUG/DEVICE INFORMATION**

This section is not applicable. We are not testing any drug or device in this proposed study. We are not proposing to develop or evaluate a new type of distress screening instrument or program, or to develop or evaluate a new psychosocial intervention or treatment.

## **7.0 SELECTION AND WITHDRAWAL OF SUBJECTS**

- 7.1 Inclusion Criteria: All patients with a visit to medical oncology for a new diagnosis of breast cancer at a study site are eligible for inclusion, with no exclusions due to gender, age, stage of disease, sequence of disease, comorbidity, spoken or written language, or other demographic or cancer characteristic.
- 7.2 Exclusion Criteria: Non-breast cancer patients.

## **8.0 STRATIFICATION/DESCRIPTIVE FACTORS/RANDOMIZATION SCHEME**

We are conducting a pragmatic cluster-randomized trial with randomization at the medical center level. There are 6 KPSC medical centers participating in total. SAS was used to generate the site randomization scheme.

## **9.0 STUDY AGENT ADMINISTRATION/TOXICITY PLAN**

This section is not applicable.

## **10.0 ASSESSMENT OF EFFICACY AND SAFETY**

This study poses minimal risk to participants, and the screening instrument (PHQ) we will be using is already in regular use within the KPSC region.

## **11.0 STUDY CALENDAR**

	Year 1 Q1-Q2	Year 1 Q3-4	Year 2 Q1-2	Year 2 Q3-4	Year 3 Q1-2	Year 3 Q3-4
IRB approval, initial study planning	X					
Randomization at center level for distress screening	X	X				
Initiate distress screening program at intervention sites		X	X			
Ongoing training and support for intervention sites		X	X	X		
Patient surveys at 3, 6, 12 months after diagnosis			X	X		
Develop interview guides; recruitment and interviews				X	X	
Qualitative coding and analysis					X	X
Implementation survey					X	X
Study wrap-up, stakeholder meetings, manuscript planning						X

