## **3.0 STUDY DESIGN**

We will use an effectiveness-implementation hybrid study design that allows for simultaneous study of the clinical effectiveness and implementation of distress screening to address the need for evidence in both areas. Hybrid designs have *a priori* focus on assessing outcomes relevant to both effectiveness of an intervention and implementation-related outcomes. We will employ a sequential mixed methods study design that integrates qualitative and quantitative methods, as is appropriate to address the proposed research questions. Our highly pragmatic approach is guided by the Pragmatic-Explanatory Continuum Indicator Summary-2 with adaptive workflow design. We will use the Consolidated Framework for Implementation Research (CFIR) to guide collection and analysis of implementation outcomes.

[figure not shown]
We will use cluster randomization at the medical center level. There will be 6 KPSC medical centers participating in total: 3 intervention sites and 3 control sites.

The screening program will be implemented at the 3 intervention sites, offering the program to all newly diagnosed breast cancer patients within the intervention site over a 12-month period with no exclusions. Under the intervention condition, distress screening using the Patient Health Questionnaire (PHQ), available in the electronic record, will be offered to patients in clinic (paper-based surveys or completed online with the assistance of the LVN, MA, RN or other member of the clinical team administering the screening). Patients are free to refuse distress screening.

Control condition patients will receive the current standard of care (ad hoc distress screening at the clinician's discretion) and basic education about the study. Control sites will not be prohibited from using the PHQ. We anticipate a total sample of 1,200 newly diagnosed patients, 600 in each arm.

Intervention sites will receive audit and feedback of performance data and implementation facilitation throughout the 12-month intervention period (implementation strategies).

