- 4.4 **Method of screening:** We are using PHQ, a recommended distress screening instrument (the PHQ is available in multiple languages). This instrument has been shown to be a valid, reliable tool with high sensitivity and specificity for measuring distress in the cancer population. The instrument is also credible and acceptable to KPSC clinicians and the PHQ are already built into the KPSC electronic health record. The screening will be offered as part of usual care at the intervention sites. Patients are free to refuse distress screening.
- 4.5 **Adaptive workflow design and responsibility of screening program:** We have developed an adaptive approach to the screening workflow, where the screening process can be completed differently at intervention sites depending on local context and resources. While the timing of the screening (e.g., initial visit, follow-up visit), instrument, scoring, and referral algorithm remains the same across all intervention sites, the type of staff overseeing the screening, screening mode (e.g., on paper, entered into computer), and place of screening during the visit (e.g., while in waiting room, while in exam room) can vary. As recommended in the guidelines, we have identified specific staff embedded in the oncology breast care teams to be the main points of contact for the screening program. These staff include: Oncology Department Administrators (DAs) and Assistant Department Administrators (ADAs), as well as oncology RNs, LVNs, MAs, and social workers where appropriate. Accountability and oversight of screening at each site can

vary per local context. We have provided ongoing training and support to the clinical care teams identified at each intervention site (implementation facilitation).

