- 4.8 **Identification of participants for patient-reported outcome surveys.** All eligible patients who speak English or Spanish will be invited to participate in a survey of patient-reported outcomes. We will confirm if the potential participant has an active email address via our membership databases. Those who do will be initially contacted via email; those who do not will be initially contacted via postal mail (see contact workflow descriptions, below). Those who agree to participate will be asked to complete these two brief surveys at 3 time points (3-, 6- and 12-months). We will alert the oncology teams at all participating medical centers, as well as KPSC Member Services, in advance so that they are aware of the survey administration schedule and prepared to address any patient questions about the surveys and/or the study.
- 4.9 **Survey administration and tracking:** We will use RedCap software for all recruitment and survey tracking, as well as for on-line consenting and administration of the surveys whenever possible (e.g., for all patients with a viable email address), as well as for tracking postal mail and phone recruitment contact attempts.
- 4.10 **Outcomes:**

Primary. Our primary outcome is percent of eligible patients screened and referred (based on PHQ score) at intervention versus control sites.

Secondary. Our secondary outcomes include: completion of recommended referrals, utilization of outpatient medical oncology visits, primary care visits, behavioral health visits, urgent care visits, and emergency department visits; we will also examine patient-reported outcomes using the Functional Assessment of Cancer Therapy-Breast survey, and the Breast Cancer Prevention Trial (BCPT) Symptom Checklist.

***Please note: We received a waiver of written informed consent for the electronic health record data collection aspect of the study to identify newly diagnosed breast cancer patients at intervention and control sites during the screening intervention period (12 months) on September 22, 2016; we received a waiver of written informed consent for the survey portion of the study on May 8, 2017.***

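### Does the study calendar cut off the 12-month patient surveys by marking survey work in Year 2 only?

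*Combined protocol and SAP*

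**What the plan says.** In section 11.0 the row "Patient surveys at 3, 6, 12 months after diagnosis" is marked for Year 2 Q1-2 and Year 2 Q3-4. The Year 1 and Year 3 columns of that row are blank. The row "Initiate distress screening program at intervention sites" is marked for Year 1 Q3-4 and Year 2 Q1-2.

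Section 3.0 sets the intake: "offering the program to all newly diagnosed breast cancer patients within the intervention site over a 12-month period". The consent note under section 4.10 applies the same 12-month identification period to control sites.

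Section 4.8 invites every eligible patient who speaks English or Spanish to be surveyed at 3, 6 and 12 months. Sections 5.5 and 13.5 repeat the three time points, and section 14.2 counts them from diagnosis. Section 4.9 describes the tracking: "We will use RedCap software for all recruitment and survey tracking".

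**The concern.** A cohort that takes a year to assemble and is then followed for a year cannot be surveyed inside a single 12-month block. Read literally, the calendar has survey work stop at the end of Year 2, before patients diagnosed in Year 2 reach 12 months.

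The surveys at issue are the FACT-B and the BCPT Symptom Checklist, both secondary outcomes under Aim 1. If field staff or funding followed the grid, a large part of the 12-month wave would be missing. The primary outcome (screening and referral) comes from the electronic record and would not be touched. The cut would depend on calendar date and apply to both arms alike, so the main cost would be precision at 12 months rather than bias between arms.

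**Working it through.** **Inputs.** Months are counted from study start, so Year 1 Q3-4 is months 6-12, Year 2 is months 12-24 and Year 3 is months 24-36.

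- Marked survey row: months 12-24 (section 11.0).
- Earliest programme start: month 6 (section 11.0).
- Intake: 12 months (sections 3.0 and 4.10).
- Surveys: 3, 6 and 12 months (sections 4.8, 5.5, 13.5) after diagnosis (section 14.2).
- Assumptions, not in the documents: uniform entry, and a lag L of 0 to 1 month from diagnosis to the oncology visit that brings the patient into the cohort.

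**Length marked.** Two half-years: 2 × 6 = 12 months.

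**Length needed.** If intake starts at month s and L = 0, the first survey is at s + 3 and the last at s + 12 + 12 = s + 24. The span is (s + 24) − (s + 3) = 21 months for any s. A constant lag leaves this unchanged. A lag that varies between 0 and 1 month stretches it to at most (s + 24) − (s − 1 + 3) = 22 months.

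**Placement with s = 6.** At L = 0, surveys run from month 9 to month 30. At L = 1, they run from month 8 to month 29. Either way some fall in Year 1 Q3-4 and some in Year 3 Q1-2, and neither is marked.

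**Share outside the row, s = 6.** A patient entering at month e has the survey for time point v at e − L + v.

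| Survey | Falls outside when | L = 0 | L = 1 |
|---|---|---|---|
| 12-month, after month 24 | e > 12 + L; share (6 − L)/12 | 50% | 42% |
| 3-month, before month 12 | e < 9 + L; share (3 + L)/12 | 25% | 33% |

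**Can any reading make the row fit?** Ending by month 24 needs s + 24 ≤ 24, so s = 0. The calendar has only approval, planning and randomization in those first six months, and the first surveys would then fall at month 3, again outside the row. A 6-month intake from month 6 would end at 6 + 6 + 12 = 24, but it contradicts the stated 12 months. The mismatch therefore cannot be read away.

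**Which statement governs?** On one side is one row of boxes. On the other, four sections state the three time points, and section 4.8 extends the invitation to every eligible English or Spanish speaker. No section limits the surveys to early entrants or gives a stop date. The grid also has no row for the retrospective referral data or the 18-month utilization data of sections 5.2 and 5.3, or for the quantitative analysis of section 14.2, yet nobody would take those as cancelled. It reads as an indicative project timeline rather than a fieldwork schedule.

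**The case for a change.** The strongest case for a change is that calendars drive staffing and budgets. This row names the 12-month wave itself, so it cannot be taken to show only the survey launch, and no entry date reconciles it with the text. The edit would be trivial.

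The position could also be worse than the month-6 figures suggest. The row "Ongoing training and support for intervention sites" spans months 6-24. Section 4.5 identifies such support with implementation facilitation, and section 3.0 says "Intervention sites will receive audit and feedback of performance data and implementation facilitation throughout the 12-month intervention period". On that reading intake could start as late as month 12, with the last surveys at 12 + 24 = month 36, the end of the third year.

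The arithmetic in the first paragraph stands. The later start is weakly supported. The support row covers 18 months while facilitation is tied to a 12-month period, so the row may include training before launch and cannot fix when intake begins. The initiation row covers exactly 12 months, months 6-18, which matches the stated period and points to a month-6 start.

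The feared harm requires staff to follow an incomplete grid against the survey text, while the survey system tracks recruitment and surveys. Nothing in the documents shows that the 12-month surveys were meant to stop, so omitted boxes are the likelier explanation. Even if some were lost, the mixed model in section 14.2 is meant for incomplete repeated measures and would recover part of the information from the earlier waves. How much precision would go cannot be said, because it depends on response rates and on the correlation between waves, and the documents give neither.

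**Conclusion.** The calendar and the text do disagree: 12 months of survey work are marked and about 21 are needed, so surveys run into Year 3 for every start the calendar allows. For a month-6 start, about 42-50% of 12-month surveys and 25-33% of 3-month surveys lie outside the marked boxes. Those shares rest on uniform entry and a lag of 0 to 1 month.

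This is a clerical slip. The text settles what is to be done: every eligible English or Spanish speaker is invited, at all three time points, counted from diagnosis. A study team working from it would continue the surveys into Year 3, and the analysis in section 14.2 already presumes all three waves. Extending the row would tidy the document without altering who is surveyed, when, how the data are analysed or what can be concluded. No change to the plan is called for.
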